4.3. Anaphylaxis Study Stopping Rule

If at any point during the study $\geq 10\%$ of patients experience an anaphylactic event, the anaphylaxis study stopping rule will be executed. The study stopping rule will halt any additional enrollment into the study for safety purposes. Additionally, any planned study drug administration to randomized patients will be immediately discontinued. The remaining study procedures and visits may be performed if deemed necessary by the Sponsor.

4.4. Temporary Discontinuation of Study Intervention

Participants may have their study drug administration temporarily suspended during the course of the study. Study drug administration should be temporarily withheld if the participant experiences one or more of the following:

- ALT $>3\times$ ULN (moderate)
- Neutrophils $<1000/\text{mm}^3$ (severe)
- Platelet count $<50,000/\text{mm}^3$ (severe)
- Platelet count $<75,000/\text{mm}^3$ (moderate) with evidence of concurrent TIMI major bleeding.

Laboratory measures should be present on two independent assessments. After a temporary suspension of study drug has been performed, study drug may be restarted provided the participant has met the following criteria:

- Neutrophils $\geq 1500/\text{mm}^3$, and
- Platelets $\geq 100,000/\text{mm}^3$

No ongoing clinical sequelae attributable to neutropenia or thrombocytopenia, respectively. If,

after restarting study drug, the event causing temporary discontinuation reoccurs study drug should be discontinued permanently.

4.5. Patient Discontinuation/Withdrawal From the Study

The following are descriptions of patient discontinuation and withdrawal from the study. This is not an exhaustive list, and each instance should be evaluated on a case-by-case basis.

- Withdrawal of consent. A patient may elect to withdraw consent to treatment at any time;
- Patients withdrawing their consent for all study procedures must be given the option to continue to give consent for passive follow-up (ie, by means of chart review) for AEs;
- Patients discontinuing study drug treatment after receiving any amount of study drug should undergo all early termination (ET) and safety follow-up study procedures per the Schedule of Procedures (Appendix A) unless the patient also explicitly withdraws consent for these procedures as mentioned above. If patients discontinuing during the Safety Follow-up Period, conduct procedure per the Schedule of Procedures for ET2. The study drug has a long PD effect. Therefore, continued monitoring for PD effects and safety is prudent;
- A patient may be withdrawn at any time at the discretion of the Investigator for safety, behavioral, compliance, or administrative reasons. Participation in the ET and safety follow-up procedures will be evaluated on a case-by-case basis. If possible, patients should take part in the ET and safety follow-up procedures in the Schedule of Procedures (Appendix A);
- If the patient withdraws consent for disclosure of future information, the Sponsor may retain and continue to use any data collected before such a withdrawal of consent; or
- If a patient withdraws from the study, the patient may request destruction of any samples taken and not tested. The Investigator must document this in the site study records.

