5.6. Management of Specific Adverse Events

5.6.1. Injection-Related Reactions, Hypersensitivity, and Anaphylaxis

Patients will be carefully monitored for 1 to 2 hours at the site post every dosing. If any safety concerns are observed between the first and second doses, the Investigator/Sponsor will investigate the discontinuation of further doses and/or the entire study.

Signs of a possible injection-related reaction include fever, chills, pruritus, and urticaria.

Anaphylaxis is a severe, potentially fatal, systemic allergic reaction that occurs suddenly after contact with an allergy-causing substance, such as an investigational product.

For the purposes of this study, a hypersensitivity reaction is defined as an acute onset of an illness with involvement of the skin, mucosal tissue, or both during injection of the study drug (but does not meet the definition of anaphylaxis described above).

If signs and symptoms of injection-related reactions are observed and the patient's cardiovascular status is stable, treat the patient as follows:

- If the patient continues to show signs and symptoms of hypersensitivity, administer an SC dose of antihistamine, if the Investigator believes this is appropriate.
- In patients who have experienced mild or moderate injection reactions in the past or there is concern that the patient may develop an injection reaction, antihistamines and/or acetaminophen may be administered prophylactically prior to subsequent injections, at the discretion of the Investigator.
- In patients who experience severe (Common Terminology Criteria for Adverse Events [CTCAE] Grade ≥ 3) injection-related reactions, anaphylaxis, or hypersensitivity, treat the patient as follows:
 - Permanently discontinue the study drug;
 - Treat the patients as for an anaphylactic reaction with IV antihistamines, corticosteroids, epinephrine, inhaled bronchodilators, and other measures as necessary; and
 - Obtain a blood sample to determine the presence of anti-drug antibodies (ADAs).

Note: The patient should remain in the study for the End of Treatment Visit and safety follow-up.

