2.2.3 Study Drug

Ziltivekimab is supplied as a liquid for injection. Drug product is presented as a single use vial and any unused portion must be discarded.

The Ziltivekimab doses to be tested in this study are 15 and 30 mg per injection. Patients will receive subcutaneous injections of either their assigned dose of Ziltivekimab or matching placebo during the study.

Study drug is planned to be administered every 28 days for a total of 3 treatments on Day1, Weeks 4 and 8. The total cumulative dosage will be 45 mg for those patients randomized to 15 mg per injection, and 90 mg for those patients randomized to 30 mg.

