3.1.2 Analysis Visits

Scheduled visits will be assigned to analysis visits as recorded in the electronic data capture (EDC) system. If a scheduled visit is not available, unscheduled and early termination visits will be assigned to analysis visits using analysis visit windows based on the actual date the assessment took place. The low analysis day of the analysis window will be calculated as the midpoint between the scheduled assessment and previously scheduled assessment for that parameter. The high analysis day of the analysis window will be calculated as the midpoint between the scheduled assessment and the next scheduled assessment for that parameter. Where multiple measurements for a particular parameter appear within an analysis window, the scheduled visit will be used. If no scheduled visit appears in the analysis window, the result closest to the target day will be used. If equidistant and both are unscheduled and/or early

termination visits, the later result will be used for the summary measure. For applicable efficacy parameters, “End of Treatment” visit will be derived where the average of assessments at Week 10 and Week 12 visits from the EDC will be calculated. Otherwise Week 12 visit will be used as the derived “End of Treatment” visit.

Analysis Visit	Target Analysis Day	Low Analysis Day	High Analysis Day
Baseline	1		1
Week 1	8	2	12
Week 2	15	13	19
Week 3	22	20	26
Week 4	29	27	36
Week 6	43	37	50
Week 8	57	51	64
Week 10	71	65	78
Week 12	85	79	92
End of Treatment	78	65	92
Week 16	113	93	133
Week 20	141	134	148

The observational period for the study will start from informed consent and end with study completion. Any event occurring after the defined observational period, even if collected on the case report form (CRF), may not be included in the planned statistical analyses. However, all data, including that reported after the defined observational period, will be included in the patient data listings.

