3.2 Analysis Populations

3.2.1 Intent-to-Treat (ITT) Population

The ITT Population is defined as all randomized subjects and will be the primary population for analysis of efficacy data.

3.2.2 *Per-Protocol (PP) Population*

The PP population will be the secondary population for analyses of disposition, baseline data, and efficacy data. For PP population, treatment classification will be based on the randomized treatment. The PP Population is defined as all subjects in the ITT Population who completed the study and did not incur a significant protocol violation that may impact the primary efficacy assessment. Significant protocol violations may include but are not limited to:

- Failed to meet eligibility criteria
- Took the wrong study drug (i.e., did not take the randomized study drug)
- Took a restricted concomitant medication
- Failed to complete the primary efficacy assessment

A list of subjects with significant protocol violations leading to exclusion from the PP Population will be finalized prior to unblinding the randomized treatment assignments.

3.2.3 *Pharmacokinetics (PK) Population*

The PK Population is defined as all randomized subjects who receive at least one dose of study drug and have at least 1 post-dose PK serum concentration. For the PK population, treatment classification will be based on the actual treatment received.

3.2.4 *Safety Population*

The Safety Population is defined as all randomized subjects who receive at least one dose of study drug. All safety data will be analyzed using the Safety Population. For the Safety population, treatment classification will be based on the actual treatment received.

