3.4 Efficacy (Pharmacodynamic) Assessment

For all continuous efficacy variables, the number of patients (n), mean, standard deviation (SD), median, quartiles (Q1 and Q3), minimum (min) and maximum (max) values for the observed value, change from baseline, and percent change from baseline will be reported on the ITT population. The difference (Ziltivekimab - Placebo) in percent changes will be presented. For categorical efficacy variables, the number of patients and percentage will be reported on the ITT population.

Due to the known distribution of the primary and secondary efficacy endpoints, normality assumption is usually difficult to satisfy; therefore, a non-parametric approach will be used for the primary and secondary efficacy analysis. Efficacy analysis will be carried out using the Hodges-Lehmann method to estimate median differences and its corresponding 95% confidence intervals for percent change from baseline to end of treatment between each treatment arm vs. Placebo, where end of treatment is the average of assessments at Week 10 and Week 12. The p-value from the Wilcoxon test will also be presented. The nonparametric analysis will account for the covariate CKD Stage (3 vs. 4 and 5) by aligning responses within the strata defined by the covariate prior to analysis.

Sensitivity analyses will be conducted to explore the robustness of the result for primary efficacy endpoint based on mixed models for repeated measures (MMRM) analysis using log of ratio to baseline, and multiple imputation analysis on a log scale. Sensitivity analysis will also be performed based on the PP population using the non-parametric approach. Efficacy data will be summarized by randomized treatment group based on the ITT and PP populations.

The differences in proportions and 95% CIs will be based on the normal approximation to binomials.

Missing data will be imputed only in the context of sensitivity analysis as described in section 3.4.1.

The pharmacodynamic efficacy of two Ziltivekimab doses compared to placebo will be assessed by evaluating the following:

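### Patients who permanently stop study drug are not required to give hs-CRP at Weeks 10 and 12, so the unimputed primary test labelled ITT is an available-case comparison

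*Protocol*

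**What the plan says.** **After a permanent stop.** Protocol 4.5: "Patients discontinuing study drug treatment after receiving any amount of study drug should undergo all early termination (ET) and safety follow-up study procedures". The section gives no date for the ET visit and does not mention Visits 8 and 9 (Weeks 10 and 12). It adds that cases are judged individually and that continued monitoring is prudent because the PD effect is long. Appendix A puts ET1 in the same column as Week 12, with hs-CRP drawn; the follow-up visits are at Weeks 16 and 20.

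**Two other routes.** After a severe injection-related reaction, anaphylaxis or hypersensitivity, drug is stopped for good, but Protocol 5.6.1 says "The patient should remain in the study for the End of Treatment Visit and safety follow-up". After a temporary suspension, Protocol 4.4 says "study drug may be restarted provided the participant has met the following criteria" and prescribes no ET visit.

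**Analysis.** SAP 3.2.1: "The ITT Population is defined as all randomized subjects and will be the primary population for analysis of efficacy data". SAP 3.4: "Missing data will be imputed only in the context of sensitivity analysis as described in section 3.4.1". Under SAP 3.1.2, for End of Treatment, "the average of assessments at Week 10 and Week 12 visits from the EDC will be calculated. Otherwise Week 12 visit will be used". Where the planned visit is lacking, the same section falls back on dates: "unscheduled and early termination visits will be assigned to analysis visits using analysis visit windows based on the actual date".

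**The concern.** The primary endpoint needs an hs-CRP value at Week 12, or at Weeks 10 and 12. The usual route for a patient who stops drug but still consents does not ask for either. Such a patient counts in the ITT population but contributes nothing to the primary test.

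Stopping drug is unlikely to be unrelated to treatment or tolerability, so omitting stoppers can shift the estimate. With 12 patients per arm, each one omitted is 1/12 = 8% of the arm. What would be lost is the all-randomized reading of the estimate, which the SAP names as primary, and off-drug measurements that could have been taken at visits already in the schedule.

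**Working it through.** **1. Timing of the ET sample**

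Inputs:
- Dosing (SAP 2.2.3): "Study drug is planned to be administered every 28 days for a total of 3 treatments on Day1, Weeks 4 and 8".
- Visit days (Appendix A): Week 4 is Day 29 + 3 and Week 8 is Day 57 + 6, so dose 2 is due by Day 32 and dose 3 by Day 63.
- Printed windows (SAP 3.1.2): Week 4 is Days 27–36, Week 8 is Days 51–64, Week 10 is Days 65–78, Week 12 is Days 79–92, and End of Treatment is Days 65–92.

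| ET1 done at | Day | Printed window | Feeds End of Treatment? |
|---|---|---|---|
| Missed dose 2 | 29–32 | Week 4 | No |
| Missed dose 3 | 57–63 | Week 8 | No |
| A delayed date | 65–92 | Week 10 or 12 | Can count |

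The hs-CRP samples at Weeks 16 and 20 do not enter the endpoint.

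**2. SAP text against SAP table**

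The text of SAP 3.1.2 sets each window limit at the midpoint between scheduled assessments of the same parameter. In Appendix A, hs-CRP is drawn on Days 29 and 71 and not between, so the midpoint is (29 + 71)/2 = Day 50. The printed limit of 64 is the midpoint of Days 57 and 71, that is, of all visits. Under the text, an ET1 on Days 57–63 would map to Week 10; under the table it maps to Week 8. Even under the text, the SAP has no End of Treatment rule for a Week 10 value alone. An ET1 on Days 29–32 misses the window under both.

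**3. The plan's own figure**

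Protocol 9.2.5 gives a difference of −60.74, SD 16.893, and 90% power at 6 per group. The normal approximation gives n = 2(1.960 + 1.282)² × (16.893/60.74)² = 1.6, so 2 per group. The t-test reaches 90.1% at 3 per group and 99.98% at 6. The stated 90% at 6 does not reproduce, but the discrepancy is on the safe side and does not affect this point.

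**4. Size of the effect on the estimate**

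Simulation with 12 per arm: active values Normal(−60.74, 16.893), placebo Normal(0, 16.893). Of the 12 active patients, k stop and are redrawn around −60.74 × r, where r is the share of effect retained. The estimate is the median of all pairwise differences. Assumptions, none given in the documents: k, r, normal data, no CKD strata, and stoppers in the active arm only.

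| k of 12 | Stoppers omitted | r = 0 | r = 0.5 | r = 0.75 |
|---|---|---|---|---|
| 1 | −60.7 | −58.1 | −58.7 | −59.5 |
| 2 | −60.7 | −55.1 | −56.5 | −58.3 |
| 3 | −60.7 | −51.2 | −54.0 | −56.9 |

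Overstatement (stoppers omitted against stoppers kept), rounded:
- r = 0: about 3, 6 and 9.5 points
- r = 0.5: about 2, 4 and 7 points
- r = 0.75: about 1, 2.5 and 4 points

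The SD of a single trial's estimate is about 7 points.

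**5. Power**

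Wilcoxon power with stoppers kept and fully placebo-like is about 100%, 100%, 99.8% and 94% for 1, 2, 3 and 4 of 12. With stoppers omitted it is about 100%.

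**The case against.** A reader might infer that stoppers are sent to ET in place of Weeks 10 and 12, that their endpoint is missing by design, and that the primary test compares completers. The documents do not support that reading:
- Protocol 4.5 does not cancel Visits 8 and 9, gives no ET date and leaves room for individual judgement. Protocol 4.7 defines primary completion by the Week 12 visit, not by doses received, and SAP 3.3.7 tabulates reasons for injections not given.
- An ET sample dated inside the window can count.
- Temporarily suspended patients are not sent to ET, so they remain in the analysis if they attend.
- Severe reactions have their own instruction in 5.6.1. The contrast with 4.5 is not clean, because no visit in the schedule bears the name End of Treatment Visit, and Week 12 shares a column with ET1.

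The size may also be small. Protocol 4.5 refers to a long PD effect, Protocol 1.4.3 reports a half-life of 38 to 44 days (IV, hemodialysis), and Protocol 1.4.2 describes hs-CRP reduction over 8 weeks after one dose. Weeks 10 to 12 are 6 to 8 weeks after dose 2, so placebo-like is an extreme case. No subject discontinued that single-dose study.

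Finally, an MMRM and a placebo-based multiple imputation are planned.

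All of this narrows the point, but the gap stands: no text secures the Week 10 and Week 12 sample after most permanent stops. The sensitivity analyses reduce the problem without removing it. The MMRM relies on data missing at random. The imputation assumes no treatment effect in active-arm early terminators and discards their post-baseline history, which sits poorly with the stated long PD effect. Off-drug samples would replace both assumptions with data.

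**Conclusion.** The point holds in limited form. For a patient who permanently stops before dose 2 or dose 3, the Week 10 and Week 12 hs-CRP is not required. If ET1 is done at the stop, the sample normally falls before the printed window and the patient drops out of the primary analysis. The test labelled ITT is then an available-case comparison.

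The likely overstatement runs from about 1 point (one stopper, 75% of effect retained) to about 9.5 points (three stoppers, none retained). This rests on assumed counts and retention, since the documents give neither. Most of that range is at or below the sampling SD of the estimate, and power stays at 94% or more even with 4 of 12 placebo-like stoppers. What is at risk is the estimate and its interpretation, not the chance of a significant result.

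**What to change.** 1. **Protocol 4.5:** state that patients who stop study drug without withdrawing consent still attend Visits 8 and 9 on schedule, at least for the hs-CRP sample.
2. **Protocol 4.5 and 5.6.1:** reconcile the two, and say which scheduled visit the End of Treatment Visit in 5.6.1 means.
3. **SAP 3.4.1:** state that these values enter the primary ITT analysis regardless of study drug status.
4. **SAP 3.1.2:** reconcile the window text with the printed table for hs-CRP, and add a rule for when only a Week 10 value exists.

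The cost is a short amendment and one or two blood draws, at visits already scheduled, for the few patients who stop. No rule on withholding or stopping drug changes.

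### Protocol 4.5 sends a dosed patient who stops study drug to early termination and safety follow-up, and does not keep the Week 10 and Week 12 hs-CRP visits that form the primary endpoint

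*Protocol*

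**What the plan says.** Protocol 4.5 lists the kinds of discontinuation and opens with a general caveat: "This is not an exhaustive list, and each instance should be evaluated on a case-by-case basis". Two bullets matter here.

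- **Third bullet, stopping study drug.** "Patients discontinuing study drug treatment after receiving any amount of study drug should undergo all early termination (ET) and safety follow-up study procedures". The one exception is a patient who explicitly withdraws consent for those procedures. The reason given is the long pharmacodynamic effect, so that "continued monitoring for PD effects and safety is prudent".
- **Fourth bullet, withdrawal by the investigator**, whether the ground is administrative, compliance, behavioral or safety. "Participation in the ET and safety follow-up procedures will be evaluated on a case-by-case basis". It then adds: "If possible, patients should take part in the ET and safety follow-up procedures in the Schedule of Procedures (Appendix A)".

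The primary endpoint (Protocol 7.1, SAP 2.3.1) is the percent change in hs-CRP to End of Treatment, the average of Weeks 10 and 12. On dosing, SAP 2.2.3 says: "Study drug is planned to be administered every 28 days for a total of 3 treatments on Day1, Weeks 4 and 8".

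SAP 3.1.2 covers early termination values that stand in for a missing scheduled visit: "unscheduled and early termination visits will be assigned to analysis visits using analysis visit windows based on the actual date the assessment took place". In the table there, Week 10 spans Days 65–78, Week 12 spans Days 79–92, and End of Treatment spans Days 65–92. If the two-visit average cannot be formed, the stated fallback is "Otherwise Week 12 visit will be used as the derived" End of Treatment visit. SAP 3.1.5 confines imputation to the sensitivity analyses.

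**The concern.** Stopping study drug and leaving the study are different events, and 4.5 does not separate them. A patient who stops drug early but is willing to keep attending is directed to ET1 and then to the safety visits at Weeks 16 and 20. No sentence in 4.5 keeps that patient on Visit 8 (Week 10) or on Visit 9 at its scheduled time (Week 12).

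The primary analysis is on all randomized patients without imputation, so a patient with no End of Treatment value contributes nothing to it. Stops for safety or compliance may be related to treatment or to the course of inflammation, so the patients who remain may not be a random subset. With 12 per arm, one or two patients are a visible share.

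The secondary point concerns a dosed patient whom the investigator withdraws. That patient can fall under both bullets, which allow different exceptions, and the text does not say which governs.

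**Working it through.** The plan states no figure on this point, so there is none to reproduce. The check is of the visit calendar, then of the size.

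**1. What is kept after a drug stop.** From Appendix A and Protocol 6.3–6.4:

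| Visit | Day | hs-CRP scheduled | Named by 4.5, third bullet |
|---|---|---|---|
| ET1 | not dated | yes | yes |
| Visit 8, Week 10 | 71 (+6) | yes | no |
| Visit 9, Week 12 | 85 (+6) | yes | only as its alternative, ET1 |
| Visit 10, Week 16 | 113 (+6) | yes | yes |
| Visit 11, Week 20 | 141 (+6) | yes | yes |

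The patient is therefore still observed by default, but not at the two primary time points.

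**2. When the endpoint is lost.** The last in-window dose falls by Day 57 + 6 = Day 63. A patient who stops before that dose and has ET1 at the stop (an assumption) has ET1 before Day 65. Two examples, using nominal days:

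- ET1 on Day 29: the next named visit is 113 − 29 = 84 days later.
- ET1 on Day 57: the next named visit is 113 − 57 = 56 days later.

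In both, no hs-CRP falls in Days 65–92, so by the SAP table there is no End of Treatment value.

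**3. When it is not lost, or is unclear.**

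- ET1 on Days 79–92 maps to Week 12, and the stated fallback supplies End of Treatment.
- ET1 on Days 65–78 maps to Week 10. The stated fallback names only Week 12, so Week 10 alone has no rule.
- SAP 3.1.2 also says windows are midpoints between scheduled assessments of the same parameter. hs-CRP is not drawn at Weeks 6 or 8, so by that text its Week 10 window would open at (29 + 71)/2 = Day 50, not the table's Day 65. An ET1 on Days 50–64 would then map to Week 10, again with no stated rule for Week 10 alone.

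**4. Share of an arm.** One patient: 1/12 = 8.3%. Two: 2/12 = 16.7%. The documents do not give an expected number; 0 to 2 per arm is an assumption. In the single-dose study in CKD (Protocol 1.4.2) no subject discontinued.

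**5. Power.** Two-sample t test, two-sided α = 0.05, with the planning difference of 60.74 and SD of 16.893 from Protocol 9.2.5. Noncentrality = difference / (SD × √(1/n₁ + 1/n₂)).

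| Active vs placebo | SD | Noncentrality | Power |
|---|---|---|---|
| 10 vs 12 | 16.893 | 8.40 | >99.9% |
| 11 vs 12 | 33.786 (doubled, assumption) | 4.31 | 98.4% |
| 10 vs 12 | 33.786 (doubled, assumption) | 4.20 | 97.9% |

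**6. What the sensitivity analyses recover (SAP 3.4.1).** The MMRM uses the patient's earlier visits. The multiple imputation analysis treats active early terminators as having no treatment effect: it removes their post-baseline values and imputes from placebo. The per-protocol analysis excludes them. None supplies a measured Week 10 or Week 12 value.

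**The case against.** **The patient is not lost to observation.** This stands. A reader might infer that 4.5 lets a dosed patient go unobserved once drug stops. It does not: ET1, Week 16 and Week 20 are kept by default, each with hs-CRP, chemistry and hematology, and adverse events. Protocol 8.6 follows drug-related events to resolution or stabilization, 8.7 has related serious events reported after the reporting period, and 5.6.1 keeps severe-reaction patients for the End of Treatment Visit and safety follow-up.

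**The two bullets do not really conflict.** This largely stands. Both say "should", both lean toward attendance, and they address different events. Only the permitted exception differs: consent in one, case-by-case judgment in the other. What remains is that a dosed patient withdrawn by the investigator fits both.

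**The loss is not certain.** This stands. A reader might infer that every drug stop puts ET1 before Day 65. The documents do not support that: ET1 is undated, a Week 8 dose withheld under Protocol 4.4 can become a permanent stop later, an investigator may withdraw a patient at any time, and the per-parameter midpoint gives Day 50. But whether a patient has an endpoint value then depends on when the site happens to hold ET1, which is a reason to settle it.

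**Keeping off-drug visits presupposes a treatment-policy estimand, which this small study does not declare.** This does not defeat the point. Collecting the values forces no choice of estimand; they can be used or set aside by rule. Not collecting them removes the choice.

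**The SAP already handles early termination, and Week 12 alone is enough.** Partly right. The sensitivity analyses exist, and Protocol 4.7 counts a patient as complete at Week 12 despite missed interim visits. But 4.5 does not secure a Week 12 visit on schedule either.

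**Conclusion.** The concern holds in a limited form. After a drug stop, 4.5 keeps ET1 and safety follow-up but not the scheduled Week 10 and Week 12 hs-CRP. If ET1 is held at the stop and falls before Day 65, the patient has no primary endpoint value under the SAP table and leaves the unimputed primary analysis, at 8.3% of an arm per patient. This rests on the timing of ET1, which the protocol does not fix, and on how many patients stop early, which is not given.

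The consequence is possible missing-data bias, of unknown direction, in a few patients. A reader might infer a threat to power; the planning inputs do not support that. The difference between the third and fourth bullets is secondary. Minor; a cheap improvement rather than an error.

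**What to change.** Amend the third and fourth bullets of Protocol 4.5 together, along these lines:

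> Any stop of study drug, whoever decides it, ends study drug only. A dosed patient continues the remaining scheduled visits, at minimum Week 10 and Week 12 hs-CRP and the Week 16 and Week 20 safety visits, unless the patient withdraws consent for them or a documented safety or feasibility reason prevents it. ET1 is used only when the patient will attend no further treatment-period visits.

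Limit the opening case-by-case sentence of 4.5 to situations that the list does not cover.

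The cost is a short protocol amendment using visits that are already scheduled, a few more attended visits for each patient who stops drug, and slightly less investigator discretion.
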